#### The LYB Yoga intervention

Thirty participants will be randomly selected to participate in the LYB Yoga intervention ([An overview of randomization techniques: An unbiased assessment of outcome in clinical research - PMC \(nih.gov\)](#)). The Yoga sessions will be virtual and study participants will be able to complete these sessions at home. The session will not be recorded. They will be free of cost for the study participants. Yoga that will be taught is a simple form of exercise that is tailored to people with a history of TBI. The movements are slow and study participants will have the choice to participate up to their comfort level. The role of LoveYourBrain will be to administer the yoga intervention and will not be engaged in the research study.

To be included, they should:

1. Have low PTG (PGI-X score <75)
2. Be inexperienced/novice yoga users
3. Not be receiving rehab services (per [name] on 6/12/2023: exclude anyone who is receiving counseling, psychiatry, PM&R, neuro, OT, psychotherapy, social work etc.)

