#### DATA ANALYSIS PLAN

We will initially use univariate analyses and descriptive statistics to examine the frequencies and distributions of the data. Established cut-offs will be used to define the low and high PTG groups, and compare the

distribution of PTG domains, PCS, mood and PTSD between the groups. In bivariate analyses, we will use Chi-square tests ( $\chi^2$ ) to compare differences between the low PTG and high groups across various demographic and injury-related factors. Variables that meet a p-value cutoff of  $p < 0.2$  during the bivariate analyses will be included in adjusted regression models. We are using a  $p < 0.2$  cutoff instead of  $p < 0.05$  to be conservative, since this is the first exploration of PTG outcomes in a female concussion sample that we are aware of. Crude and adjusted logistic regression models will be used for effect estimates and prediction models, using a significance level of  $p < .05$

For Aim 2, we will use paired t-test to compare the mean difference in PTG scores and domains before and after the yoga intervention to determine its effectiveness. We will administer the PTG surveys again at 7 weeks and 30 days to 15 Yoga and 15 Wait list controls (see Figure 5). The 15 Yoga participants will also do the post-yoga assessments at 7 weeks. The 15 Wait list controls will do the LYB program after the 30-day PTG surveys have been completed. The 15 Wait list controls will receive a follow up survey, 1 week after the completion of the LYB program. The intervention group participants who have attended 3 or more LYB yoga sessions will also receive a week-20 follow up survey and the participants who complete the survey will receive \$30 incentive.

To evaluate the feasibility & acceptability of the intervention, we will collect the following metrics:

- A) Overall Yoga intervention **interest rate**=# interested in participating in Yoga/total # participants (how many PINK women are interested in the Yoga overall? If high can speak to using Yoga as an effective intervention for this population. If low, explore reasons)
- B) PTG-specific interest rate: #interested participants with low PTG (score <75)/total #participants (how many people with low PTG are interested in Yoga? We expect this proportion to be lower than overall metric in A above)
- C) Yoga intervention participation rate=# who enroll in LYB program (n=30)/#interested participants with low PTG (We will invite 30 people to participate so we know the numerator)

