#### INCENTIVES

Participants will receive \$40 and the 30 who participate in the Yoga intervention will receive another \$60 for completing all 6 weeks of the intervention.

For the 15 Wait list controls, who participate in the Yoga intervention and complete the follow up survey will receive \$30.

The intervention group participants who have completed 3 or more LYB yoga sessions and who have completed the week-20 follow up survey will receive \$30 incentive.

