## LIMITATIONS OF THE STUDY

First and foremost, this study is limited to female concussion survivors only and as such, is not generalizable to men who experience TBI. Secondly, the study is recruiting from the PINK concussion group, so the study cannot be generalizable to anyone not in this group, and/or all females with TBI. As this is a pilot, the Yoga intervention will have only 30 participants therefore there's the potential for Type 2 error (false negatives). We will need a larger, more powered study -ideally a clinical trial-to determine the true effect of the Yoga intervention.

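### Aim 2 tests yoga only by a before/after t-test in women selected for a low score, and does not say which survey is the wait-list women's before score

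*Combined protocol and SAP*

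**What the plan says.** Under The LYB Yoga intervention, "Thirty participants will be randomly selected to participate in the LYB Yoga intervention", and one condition for inclusion is a PTGI-X score below 75. The Data Analysis Plan gives a single effectiveness test for Aim 2: "we will use paired t-test to compare the mean difference in PTG scores and domains before and after the yoga intervention".

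The same section sets the surveys: "We will administer the PTG surveys again at 7 weeks and 30 days to 15 Yoga and 15 Wait list controls". The yoga arm's post-yoga assessment is at 7 weeks. For the other arm, "The 15 Wait list controls will do the LYB program after the 30-day PTG surveys have been completed", and afterwards "The 15 Wait list controls will receive a follow up survey, 1 week after the completion of the LYB program". Under Incentives, the wait-list women "who participate in the Yoga intervention and complete the follow up survey will receive" 30 dollars. Under Limitations, "the Yoga intervention will have only 30 participants".

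The readable text leaves four things unstated:
- which survey is the before score in each arm;
- whether the wait-list women's own yoga phase enters the paired test;
- the date from which 7 weeks and 30 days are counted;
- whether the post-programme follow-up survey contains the PTGI-X.

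**The concern.** The women are chosen on the outcome itself. Part of a score below the cut is chance, so a second measurement tends to be higher even if nothing has happened. A paired test starting from the selecting score counts that rise as a yoga effect.

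The immediate-yoga arm has no other pre-yoga score in the readable text. The wait-list women do have a later one, the 30-day survey, but the plan does not say it will be used. An analyst could test 15 women from the initial score, test all 30 from the initial score, or mix baselines across arms, and each would comply with the plan. The error rates differ greatly. The plan also has an untreated group measured over the same period, and the stated test makes no use of it.

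**Working it through.** **The plan's own figure.** No sample size, effect size or power is given for Aim 2. The stated 350 belongs to the prevalence aim and reproduces as a precision calculation if the margin is 5 points (my assumption): 1.96² × 0.35 × 0.65 / 0.05² = 349.6, rounded up to 350. Only the 35% is carried forward here.

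**Inputs**
- From the documents: selection below 75; 35% low-PTG prevalence; 15 + 15 women; a 6-week programme (Incentives).
- Assumed: normal scores; test-retest correlation ρ of 0.6 to 0.9, the same between any two surveys; two-sided 0.05, which the plan states only for the regression models; no yoga effect; no dropout. The population SD is not given, so results are in SD units.

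**Rise from the initial score**
- The cut at the 35th percentile is c = −0.385, with normal density φ(c) = 0.370, so φ(c)/0.35 = 1.058.
- Expected rise = (1 − ρ) × 1.058 SD.
- SD of change = √[(1 − ρ)² × 0.288 + (1 − ρ²)], where 0.288 is the variance of a standard normal score below the cut.
- Example, ρ = 0.7: rise = 0.3 × 1.058 = 0.32; SD of change = √(0.09 × 0.288 + 0.51) = 0.73; standardised change = 0.43.

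False-significance rates come from simulation. For the two initial-score columns, the noncentral t distribution agrees.

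| ρ | Rise (SD) | Initial score, n = 15 | Initial score, n = 30 | 30-day score, wait list, n = 15 | Pooled: 15 from initial, 15 from 30-day | Between-arm difference in change |
|---|---|---|---|---|---|---|
| 0.6 | 0.42 | 45% | 77% | 5% | 24% | 5% |
| 0.7 | 0.32 | 35% | 63% | 5% | 19% | 5% |
| 0.8 | 0.21 | 24% | 45% | 5% | 14% | 5% |
| 0.9 | 0.11 | 14% | 25% | 5% | 9.5% | 5% |

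If the SD were 20 to 30 points (assumed), the rise would be 8.5 to 12.7 points at ρ = 0.6 and 2.1 to 3.2 at ρ = 0.9. If 50% of women fell below the cut, it would be 0.32 SD at ρ = 0.6 and 0.08 SD at ρ = 0.9, with false significance of 28% and 10% at n = 15.

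**What the wait-list post-yoga survey adds.** Take a mixed model with categorical survey time, an on-yoga indicator, a common starting mean, equal correlations, and both repeat surveys of the immediate arm counted as exposed. The standard error of the yoga effect is √{(2/15) × [(1 + ρ)/2 − ρ²]}. At ρ = 0.7 this is √(0.1333 × 0.36) = 0.219 SD. Adding the wait-list post-yoga survey leaves it at 0.219, because no untreated woman is observed then and the time term absorbs the observation. A pooled paired test of 30 would have √(2 × 0.3/30) = 0.141 SD, so the model's standard error is about 1.55 times as large (1.48 at ρ = 0.6, 1.67 at ρ = 0.9).

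**Timing.** If 30 days is counted from enrolment and wait-list yoga starts promptly, a 7-week survey (day 49) on the same clock falls during the wait-list women's yoga. If 30 days follows the 7-week survey, both precede it. The text does not settle which. On either reading the 30-day survey comes before wait-list yoga, and about 6 + 1 = 7 weeks before their follow-up survey if yoga starts promptly.

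**The case against.** The strongest reply is that this is nearly a matter of missing detail. Wait-list yoga begins only after the 30-day PTG survey, so that survey is the natural before score, nothing says the initial score would be used instead, and the schedule figure, which is not shown, may label the surveys. This stands for the wait-list arm. A reader might infer that the plan must either build in a false rise or discard half its yoga data. The documents do not support that, because the 30-day survey is a third option. The reply does not help the immediate arm, which has only the selecting score before yoga.

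A second reply is that the wait-list women are called controls, so leaving their deferred yoga out of the main test is defensible. That also stands. A reader might infer that including it would double the information, since a paired test's change detectable with 80% power falls from 0.78 to 0.53 SD of change as n goes from 15 to 30. That gain belongs to a pooled uncontrolled test, which still gives about 10% to 24% false significance even with the right wait-list baseline.

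A third reply is that Limitations already presents the study as a pilot needing a larger trial. The risk disclosed there is false negatives; the bias here runs towards false positives.

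Finally, the SD and test-retest correlation are not in the documents. This is correct: only the direction of the bias follows from the plan, and its size depends on the assumed range.

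**Conclusion.** The point holds as a weakness in the choice of analysis, together with an undefined baseline. An uncontrolled paired test from a score used for selection is biased upward whenever the test-retest correlation is below 1. Under the stated assumptions the false rise is about 0.1 to 0.4 SD, and a nominal 5% test rejects in 14% to 45% of trials with 15 women and about 25% to 77% with 30. This applies to both arms, so naming the wait-list before score is necessary but does not cure the test. A comparison of change between arms over the waiting period holds about 5%.

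The documents do not show that the sponsor intends to use the initial score for the wait-list women, that their yoga data would be lost, or that a wait-list post-yoga PTGI-X score will exist.

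**What to change.** In the Data Analysis Plan:
1. Replace the paired t-test as the Aim 2 effectiveness analysis with a repeated-measures mixed model on all 30 women and the surveys already planned. Use categorical survey time and a defined on-yoga status, with the immediate arm coded as exposed from its post-yoga survey onward. Confirm that the 15/15 split is random; the readable text says this only of the selection of the thirty.
2. State that the wait-list before score is the last PTG survey completed before they start the programme (the 30-day survey), and never the initial score.
3. State the time origin of 7 weeks and of 30 days, and reconcile the two with the start of wait-list yoga.
4. Confirm that the post-programme follow-up survey includes the PTGI-X.
5. Report the wait-list change from the 30-day survey to the follow-up as a supporting, uncontrolled result (n = 15). Do not pool it with the immediate arm's change from the initial score, or claim that it doubles the precision.

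The cost is a standard error roughly 1.5 to 1.7 times that of the pooled paired test, and a little more analysis work. No new survey or payment is needed, provided the follow-up survey already contains the PTGI-X; if not, that scale must be added.

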Our study will focus on female concussions because concussions tend to be more prevalent in females, and regardless of study sample or injury mechanism (sports[12], civilian, military), women (compared to men), report greater concussion morbidity (prolonged recovery, worse physical, cognitive and psychosocial symptom reporting[13, 14], [40]), and experience poorer treatment pathways[14]. **Interestingly, women also report greater PTG after trauma, but no research has evaluated the intersection of PTG and mTBI in female concussion survivors. Not only will we be filling this gap in the field, but we will take the work further and conduct a pilot assessment of whether mindfulness based interventions such as yoga, which have been shown to improve mTBI sequelae[2], also improve PTG for individuals with low PTG in the study sample. This pilot intervention is not only important for exploring protective recovery pathways, but also aligns with emerging research advocating for exercise as medicine for concussion [2, 15, 16].**

Thus, the aims of this research are to:

Aim 1: a) Determine the prevalence of low PTG in a population of female concussion survivors.

*We hypothesize that at least 35% of the study sample will have low PTG (score <75 on PTG scale)[17]*

Aim 1b) Determine what (concussion-related factors) predict low PTG.[18]

*We hypothesize that predictors of low PTG will include: older current age[19], older age at time of injury[19], non-White race[20], history of multiple concussions, high burden of post-concussion symptoms, and high burden of mood disorders (Anxiety, depression) and PTSD*

[figure not shown]
Aim 1c) Identify which of the 5 PTG domains are least prevalent and could be targeted for future interventions.

Aim 2: a) Determine if a pilot yoga intervention improves PTG scores for individuals with low PTG.

*We hypothesize that PTG scores will increase after the yoga intervention for those with low PTG who partake in the intervention.*

Aim 2b) Identify which of the 5 PTG domains (in Aim 1c) are improved by the intervention

Figure 5: Schematic Diagram of the Project

[figure not shown]

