## Study Procedures and Assessments

### *Self-reported Measures of PTG outcomes and Domains*

**PTG assessment (primary):** We will use the 25-item scale of the PTG Inventory (PTGI-X), which has more spirituality questions [49]. Score range of 0-125, with greater scores indicating greater growth. The PTGI-X score range is from 0-5, and the cutoff point of  $\geq 3$  across items is defined as moderate-to-high PTG levels. Thus scores  $\geq 75$  (3\*25 item scale) is moderate to high on a scale of 0-125 and scores  $< 75$  are deemed low PTG [17]. The PTGI-X can be completed in 7-9 minutes.[23]

**PTG assessment (secondary):** We will additionally assess the 5 domains of PTG using the following secondary measures:

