#### POWER AND SAMPLE SIZE (based on PTG prevalence)

Using a low PTG prevalence of 35%, an alpha of 0.05 and 95% confidence interval, a sample size of 350 will provide sufficient power of 80% for the intended analyses.

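### Metric B divides interested low-PTG women by all participants, so it cannot exceed metric A or the low-PTG prevalence and does not measure interest among low-PTG women

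*Combined protocol and SAP*

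**What the plan says.** The Data Analysis Plan lists feasibility and acceptability metrics A to E. Metric A, the overall interest rate, counts women "interested in participating in Yoga/total # participants". Metric B is "PTG-specific interest rate: #interested participants with low PTG (score <75)/total #participants". The plan explains B by asking "how many people with low PTG are interested in Yoga" and adds "We expect this proportion to be lower than overall metric in A above".

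Metric C uses the number of interested low-PTG women as its own denominator. Metrics D and E concern women already enrolled in the yoga programme. No section defines an interest rate whose denominator is the women with low PTG.

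Low PTG means a PTGI-X total below 75. Aim 1a states "We hypothesize that at least 35% of the study sample will have low PTG". The Power and Sample Size section plans 350 participants "Using a low PTG prevalence of 35%, an alpha of 0.05 and 95% confidence interval".

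**The concern.** The label and the attached question ask for a conditional rate: among women with low PTG, what proportion wants yoga? The formula gives a joint proportion: among all respondents, what share both has low PTG and wants yoga? That figure mixes how common low PTG is with how interested those women are.

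Because A and B share a denominator and B counts a subset of A's women, setting B against A can come out only one way, or tie. The result is fixed before any data arrive. Low PTG is an entry condition for the yoga component, so interest in this group is a natural feasibility question, and none of the listed metrics answers it. A reader who takes B at its label could conclude that low-PTG women are less keen than average when they are keener.

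**Working it through.** **Inputs.** N = 350 (minimum target, Number of Subjects and Power and Sample Size). Low-PTG prevalence 0.35 (same sections; Aim 1a says at least this). Definitions of A and B from the Data Analysis Plan. The documents give no interest rates, so those below are assumptions.

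**The plan's own figure.** N = 350 reproduces as a precision calculation for one proportion, if a margin of 5 percentage points is assumed (none is stated):

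n = 1.96² × 0.35 × 0.65 / 0.05² = 349.6, rounded up to 350.

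A margin of 4 points gives 547 and one of 6 points gives 243. The plan states no value for A or B, so there is nothing further to reproduce.

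**Bounds.** Let L be the number of women with low PTG, x the interested women among them (0 ≤ x ≤ L), and y the interested women scoring 75 or more (y ≥ 0). Then

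- A = (x + y)/N
- B = x/N
- B ≤ A, with equality only when y = 0
- B ≤ L/N, the observed prevalence
- interest among low-PTG women = x/L = B ÷ (L/N)

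At 35%, 0.35 × 350 = 122.5. Taking L = 122 leaves 228 others, and B is capped at 122/350 = 34.9% even if every low-PTG woman is interested.

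**Enumeration.** With x from 0 to 122 and y from 0 to 228 there are 123 × 229 = 28,167 possible outcomes. None gives B above A or above the prevalence. B equals A in 123 of them, all with y = 0.

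**Assumed interest rates, N = 350, L = 122.**

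| Low PTG | Others | A | B as written | x/L |
|---|---|---|---|---|
| 20% | 60% | 46.1% | 7.0% | 20% |
| 50% | 50% | 50.0% | 17.4% | 50% |
| 80% | 40% | 53.9% | 27.9% | 80% |
| 100% | 50% | 67.4% | 34.9% | 100% |

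The third row, for example: A = (0.8 × 122 + 0.4 × 228)/350 = 188.8/350, and B = 97.6/350. B is below A in all four rows, although low-PTG women are less interested in the first, equally interested in the second, and more interested in the last two. When interest is unrelated to PTG, B is simply prevalence × A, here 0.349 × 50% = 17.4%.

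**Sensitivity to prevalence.** With the same 80% and 40%, a prevalence of 50% gives A = 60.0% and B = 40.0%; a prevalence of 65% gives A = 66.1% and B = 52.1%. The cap rises with prevalence and the inequality remains.

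**Precision of the corrected rate.** The 95% half-width with 122 women is 1.96 × √(0.5 × 0.5/122) = 8.9 points at a rate of 50%, and 8.1 points at 30% or 70%. For the difference between the two groups at 50% each, it is 1.96 × √(0.25/122 + 0.25/228) = 11.0 points.

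**The case against.** The strongest defence is that A, B and C form a recruitment funnel: interested out of all, interested with low PTG out of all, then enrolled out of those. B × C is then the share of all respondents who enrol. Read so, B is a valid yield figure, useful for working out how many women must be surveyed, and the remark that it will be lower than A only notes that a subset is smaller. This stands as far as it goes. It does not rescue the label or the attached question, and it leaves the expectation empty.

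It is also fair to say that nothing is lost for good: dividing B by the prevalence from Aim 1a gives the wanted rate. And the 35% cap is conditional, since it moves with the prevalence observed.

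Three stronger readings are tempting, and the documents support none of them.

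- A reader might infer a planned test of B against A. The plan gives only an expectation in parentheses, with no test, threshold or decision rule.
- A reader might infer that the study will report low-PTG women as less interested. No section plans that conclusion; it is a misreading the label invites.
- A reader might infer that the case for a larger trial rests on B. The Limitations section bases that call on the risk of false negatives with 30 participants and does not mention interest rates. Only metric A carries guidance on what a high or low value would mean.

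**Conclusion.** The concern holds as a mismatch between a metric's denominator and the question it is meant to answer. For any data, B is at most A and at most the low-PTG prevalence, so the expectation that it is lower than A can only hold or tie. Read as an interest rate, B can show the opposite direction to the truth: 27.9% against 53.9% when low-PTG women are twice as interested as the others.

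The bounds are algebra and rest on no assumed rate, only on A, B and the prevalence being counted over the same participants. The illustrative percentages rest on assumed interest rates and, in the main table, on 35% prevalence. The documents hold no interest data, so the distortion that would occur in practice is unknown.

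The consequence is limited to one descriptive feasibility metric. The prevalence, predictor and pre-post yoga analyses under Aims 1 and 2 are unaffected. The change is worth making because it is cheap and lets the pilot answer its own question.

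**What to change.** In the Data Analysis Plan:

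1. Define the PTG-specific interest rate as interested participants with PTGI-X below 75, divided by all participants with PTGI-X below 75.
2. Report beside it the same rate for participants with PTGI-X of 75 or above, and compare the two, with a confidence interval for the difference.
3. Leave metric A as it is.
4. If the present quantity is wanted, keep it under a recruitment-yield label: the share of all respondents who have low PTG and are interested.
5. Delete the expectation that B is lower than A, or restate it for the two group-specific rates.
6. State how participants without a PTGI-X total are counted. Survey questions are voluntary, so the denominators may otherwise differ.

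The cost is a few lines of text. Metric A and Aim 1a already require interest and PTG score, so no new data are needed. The one drawback is the smaller denominator, about 122 of 350 at 35% prevalence, with a half-width of 8 to 9 points for rates between 30% and 70%. The new rate describes all low-PTG respondents. It is not the rate among women eligible for yoga, who must also be yoga novices and not receiving rehabilitation services, and the report should say so.

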We are requesting a waiver of documentation of consent as participants will be recruited online using an IRB approved consent form that will be on the study's landing page. Upon clicking the survey invitation link, potential survey takers will be brought to the very first page of the survey which will be the IRB-approved consent page. This will list the risks, benefits, incentives, and overall research processes. The consent will also state that the research is no greater than minimal risk and involves procedures for which written consent is normally not required outside of the research context. After reviewing the approved information sheet, participants will be prompted to consent yes in order to move on to the survey body. Those who do not consent will be sent to a "Thank you page" and not continue. Those who do so, will begin the survey. All survey questions will be voluntary and responses will be de-identified and analyzed in aggregate to ensure anonymity.

We are also requesting a waiver of Vincent cards for incentives, as we will be using e-gift cards for providing incentives to the study participants. We will collect PHI (full name, email, address, etc.) to incentivize participants. Collected PHI will be removed in the final data set, after all incentives are provided to those who complete the study, including the Yoga intervention (if they are selected). PHI will not be reused or disclosed to any other person or entity outside of the scope of this research except (i) as required by law, (ii) for authorized oversight of the research study, or (iii) for other research for which the use or disclosure of PHI would be permitted by the HIPAA Privacy Rule.

- a) **Number of Subjects:** We seek to have at least 350 participants using an alpha of 0.05, 95% confidence interval and a low PTG prevalence of 35%.
- b) **Gender and Age of Subjects:** To be eligible for this study, participants must be at least 18 years of age. There is no gender or gender identity restriction.
- c) **Racial and Ethnic Origin:** Enrollment will not be based upon racial or ethnic origin.

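### The yoga participation rate (metric C) presets its numerator to the 30 women invited and divides by all interested low-PTG women, so as written it does not measure uptake

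*Combined protocol and SAP*

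**What the plan says.** The DATA ANALYSIS PLAN lists feasibility and acceptability metrics A to E. Metric C reads "Yoga intervention participation rate=# who enroll in LYB program (n=30)/#interested participants with low PTG", and the reason given for the preset figure is "We will invite 30 people to participate so we know the numerator".

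The section on the LYB Yoga intervention says how the 30 arise: "Thirty participants will be randomly selected to participate in the LYB Yoga intervention". The analysis plan splits them into "15 Yoga and 15 Wait list controls". Besides low PTG, entry to the yoga part requires women to "Be inexperienced/novice yoga users" and "Not be receiving rehab services". Neither condition appears in metric C's denominator.

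The neighbouring metrics are:
- **A:** interested women over all participants.
- **B:** "interested participants with low PTG (score <75)/total #participants".
- **D:** a completion rate written as the number enrolled (again n=30) over the number who complete.

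The plan states no rate of acceptance among women invited, no count of refusals and no rule for replacing a woman who declines.

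**The concern.** A participation rate should say what share of the women offered the program took it up. Metric C departs from this in two ways.

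1. The numerator is declared known before anyone has replied, because it is the number of invitations. Followed literally, a woman who declines is still counted as enrolled.
2. The denominator is not the group that received the offer. It contains interested women who were not drawn in the random selection and, as worded, women who would not qualify for the yoga part.

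What remains is a quota of places divided by demand. Metric A treats high interest as a favourable sign, yet the same interest pushes metric C down.

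The LIMITATIONS section calls for a larger study, ideally a clinical trial. Uptake per invitation is a figure the planners of that study would need, and this metric would not give it to them.

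**Working it through.** **Inputs from the documents**
- Preset numerator: 30 (metric C). It agrees with the two groups: 15 + 15 = 30.
- Survey size 350 and low-PTG prevalence 35% (Population and Recruitment; POWER AND SAMPLE SIZE). As a side check, 1.96² × 0.35 × 0.65 / 0.05² = 349.6, which rounds up to 350. The half-width of 5 points is my assumption; the plan does not state one.
- The plan gives no value for metric C itself, so there is no rate to reproduce.

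**Assumed, because the documents give no figure**
- The share i of low-PTG women who are interested, varied from 25% to 100%.
- The number of invited women who enroll, varied from 15 to 30.

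**Step 1. Size of the denominator.** 350 × 0.35 = 122.5, about 122 low-PTG women.

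**Step 2. Metric C as written.** C = 30 / (122.5 × i).

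| Interest i | Interested low-PTG women | C |
|---|---|---|
| 25% | 30.6 | 98% |
| 40% | 49.0 | 61% |
| 50% | 61.2 | 49% |
| 75% | 91.9 | 33% |
| 80% | 98.0 | 31% |
| 100% | 122.5 | 24% |

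C falls steadily as interest rises. The direction does not depend on the assumed levels. It follows from a fixed numerator over a growing denominator.

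**Step 3. Effect of refusals.** Take 50% interest. If 30, 24 or 18 of the 30 invited women enroll, uptake among those invited is 30/30 = 100%, 24/30 = 80% or 18/30 = 60%. With 30 entered in advance, C is 49% in all three cases.

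**Step 4. If the label governed instead.** Counting actual enrollees, 20 enrolling at 50% interest gives 20/61.2 = 33% rather than 49%, so refusals would show. At 75% interest the same 20 give 20/91.9 = 22%. The fall with interest remains, and never-invited women stay in the denominator.

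**Step 5. Can another metric recover uptake?** A and B count interest only. D reuses n=30 as the number enrolled. It is also written with completers underneath, so it cannot fall below 1, and it does not separate women who declined from women who started and stopped.

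**Step 6. The replacement ratio.** Enrolled over invited, with 30 invited and Wilson 95% intervals:

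| Enrolled of 30 invited | Rate | 95% interval |
|---|---|---|
| 15 | 50% | 33% to 67% |
| 20 | 67% | 49% to 81% |
| 25 | 83% | 66% to 93% |
| 30 | 100% | 89% to 100% |

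This ratio falls with refusals and does not depend on how many other women were interested.

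**The case against.** **The label says enroll.** The preset 30 could be read as a planned count, to be replaced by the actual number. A reader might infer that refusals cannot lower the rate under any reading, and that goes too far: label and preset value conflict, and if the label governed, refusals would count. But the stated reason for the 30 is the number of invitations, which favours the literal reading. The label reading also leaves the denominator problem in place (Step 4).

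**Decliners might be replaced until 30 enroll.** No such rule is stated. If one were applied, the numerator would be 30 again and refusals would still not show.

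**Later drop-out belongs elsewhere.** This stands. A woman who enrolls and withdraws before her first session, including a wait-list woman before her turn, is properly counted as enrolled; her loss belongs with completion. The loss specific to metric C is refusals. Requiring attendance at one session is a possible definition of participation, not the only correct one.

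**A ratio of places to demand must fall as demand rises, and interest is reported in A and B.** True, and the ratio is legitimate as a description of how much demand the pilot can serve. It is not participation.

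**Eligibility may be screened before interest is asked.** Figure 5 was not visible in the text reviewed, so the order of screening is unknown. The written denominator names only interest and low PTG. How many ineligible women it would include cannot be determined.

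**Conclusion.** The point holds. As written, metric C equates invited with enrolled and divides by women who were not all offered a place, so it does not measure uptake. No other listed metric does.

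The size is illustrative: 49% at 50% interest against 31% at 80%, with the rate unmoved by whether 30 or 18 of those invited accept. These figures rest on 350 respondents, 35% low PTG and assumed interest and enrolment. The direction does not rest on the assumed values.

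A reader might infer that this undermines the yoga evaluation as a whole. The documents do not support that. Feasibility is not among the numbered aims, no threshold or decision rule uses metric C, and the paired comparison of PTG scores is unaffected. It is a descriptive metric that should be fixed.

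**What to change.** Remove the preset 30 from metric C. Define participation as the number of women who actually enroll divided by the number of eligible women invited: low PTG, interested, yoga novices and not receiving rehab services. If a woman who declines is replaced, count both her and her replacement in the denominator. Report the numbers invited, declined and never started beside the rate.

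The present ratio may be kept under another name, as places per interested low-PTG woman. First-session attendance and figures by arm are optional. At 15 per arm they are imprecise: 12 of 15 is 80%, with a Wilson 95% interval of about 55% to 93%.

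The cost is a wording change and a simple log of invitations and replies. A reader might infer that the incentive rules already supply these data. They do not: the INCENTIVES section ties the yoga payments to taking part in or completing sessions and to follow-up surveys, and none of them needs a record of invitations or refusals. The log should be kept as invitations go out, because refusals may be hard to reconstruct later. The reported rate may be less favourable than the preset one.
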